## R36 Protocol and Analysis Plan

**Protocol #:** 18-1675

**Project Title:** Underutilization of Hospice in Older African Americans

**Principal Investigator:** [name]

**Mentor:** [name]

**Version Date:** 0124/19

**I. Hypotheses and Specific Aims:** The goal of this study is to determine if poor health literacy and/or insufficient knowledge of hospice care are barriers preventing African Americans from understanding what hospice care is and negatively influences their opinions of hospice care. Additionally, the study will evaluate the influence of perceived discrimination and mistrust in healthcare on hospice knowledge and attitudes and beliefs towards hospice care.

**Aim 1:** To evaluate the relationship between literacy, mistrust and perceived discrimination on hospice knowledge and hospice beliefs and attitudes in older African Americans.

**Aim 2:** To evaluate the effect of hospice decisional support materials on hospice knowledge and attitudes and beliefs about hospice in older African Americans.

## II. Background and Significance:

Research demonstrates that African Americans fail to enroll in hospice services, even though they disproportionately suffer more aggressive forms of, and experience more disability from, the diseases most common among hospice enrollees. The increasing number of people of color living with debilitating chronic disease and the continued growth of healthcare expenditures threatens to financially overburden Medicare. By the year 2050, African Americans will comprise nearly 12% of Americans over the age of 65. These factors create a significant need for interventions to increase hospice utilization in aging African Americans.

There is limited research that explores the reasons driving underutilization of hospice services among African Americans. Many researchers reduce the disparity to religious and/or cultural beliefs and an inherent preference for more aggressive treatments. Although these may be legitimate barriers, another plausible barrier to hospice utilization is health literacy and a diminished or inaccurate knowledge of hospice care.

African American patients routinely report misconceptions and deficiencies in knowledge about hospice care. Patients report they do not receive information on hospice from healthcare providers and receive misinformation from family and friends. Studies suggest that White providers are less likely to provide information about hospice services or refer their African American patients to hospice. Other cultural barriers for African Americans include an emphasis on informal or family caregivers and family-centered decision making, and the importance of integrating religious and spiritual values into care plans. Hospice incorporates family-centered care models and accommodates patients' religious and spiritual beliefs, but this core piece of information may not be adequately communicated to African American patients. Inaccurate and inadequate information about hospice prevents patients from understanding the full scope and range of hospice services.

Limited knowledge about hospice and the misconceptions of hospice care are health literacy barriers which may be mitigated with a patient decision aid designed to provide accurate and unbiased information about hospice care. Patient decision aids are evidence-based interventions that promote knowledge production, patient-centered care, decisional autonomy, and reduce decisional conflict in medical decision making. This study will test hospice decisional support materials (e.g. hospice paper decision aid and hospice video decision aid) that will potentially address knowledge and literacy barriers to hospice use among African Americans. The decisional support materials conform to the rigorous standard of the Internal Patient Decision Aid Standards (IPDAS), which is an organization that ensures the production of high-quality patient-centered decision aids.

This study hypothesizes that low health literacy correlates to low hospice knowledge. This hypothesis builds on prior work by Volandres and colleagues which demonstrates poor health

literacy is a stronger predictor of end of life choices than race. These studies focused specifically on end of life decisions in patients with dementia. Some scholars criticize the Volandes team's work for producing heavily biased videos that show graphic representations of end-stage disease and treatments that shock patients into choosing hospice. The goal of the current project is to use a neutral decision aid representing the benefits and disadvantages of hospice. The content of this decision aid heavily relied on input from stakeholders such as patients, caregivers and the diverse variety of providers who care for hospice patients. The decision aid presents general information about hospice and is not disease specific, unlike Volandes' decision tools.

Additionally, this study hypothesizes that standing paradigms of discrimination perpetuate a systemic mistrust in healthcare. African Americans were systematically and intentionally excluded from healthcare and the evolution of the modern healthcare system. From pre-slavery America through the middle of the 20th century, American physicians were trained to believe African Americans were a different species. This racist thinking allowed medical professions to abuse and experiment on African Americans with impunity. These practices bred and nurtured the mistrust African Americans feel towards the healthcare system and healthcare professionals, and by extension may negatively influence knowledge and perceptions of hospice care. Decision aids may help lessen mistrust and improve perceptions of hospice.

### **III. Preliminary Studies/Progress Report:**

We conducted and extensive qualitative needs assessment and environmental scan of available hospice decision aids. Though the needs assessment we interviewed 5 patients, 20 caregivers and 27 providers (e.g. social workers, nurses, chaplains) regarding their perceptions of participating in hospice. In the preliminary analyses, we found that all participant groups describe misunderstandings and myths regarding hospice care consistent with those cited in the literature. Additionally, we learned that timing of introduction and initiating of hospice care was a major theme across all participants. Hospice is often presented as an option only when death is imminent. As a result, caregivers expressed regret for not being aware of or enrolling their loved ones in hospice earlier in the disease course.

People from varying different backgrounds, races/ethnicity and cultures participated in the qualitative needs assessment. Overwhelmingly participants from diverse race and ethnic backgrounds felt a hospice decision aid would facilitate end of life discussions within their communities. Study participants felt any hospice PtDA should focus on providing clear and accurate information about hospice care to help them navigate the ubiquitous misunderstanding and misperceptions of hospice care. Participants advocated for a neutral balanced tool that clearly explained the pros and cons of hospice, detailed the eligibility requirements and accurately described the payment mechanisms for hospice care.

Our environmental scan found only 7 PtDAs that mentioned hospice as a potential secondary treatment option for people with illnesses such as end stage heart failure, cancer or kidney disease. The PtDAs did not describe the eligibility criteria hospice, the services provided by hospice and failed to provide resources for patients interested in hospice care. These PtDAs inadequately explain the nuances of hospice care as a primary treatment option and have limited reach to only specific populations. Further, these PtDAs fail to acknowledge the complexity of end-of-life decision making.

We then brought in 20 laypersons into our lab to conduct an organic web search for information regarding hospice and to participate in a semi-structured interview regarding their perceptions of the available information. Many of the online resources that the participants found were promotional materials from specific hospices or other special interest groups, thus the participants found these materials confusing and biased. Further, the online resources failed to provide clear information on cost, enrollment, and lacked the desired patient and caregiver testimonials. Surprisingly almost all participants went to sites such as yelp to get narrative descriptions of hospices.

### **IV. Research Methods**

#### **A. Outcome Measure(s):**

Overview: The goal of this study is to test whether or not hospice decisional support materials can improve hospice knowledge and attitudes and beliefs towards hospice in older African Americans.

Primary Outcomes: There are three primary outcomes for the study which are change in hospice knowledge measured by the Hospice Knowledge Survey, change in opinions attitudes about hospice care measured by the Hospice Beliefs and Attitudes Scale (HBAS) and decision self-efficacy will be measured the Decision Self-Efficacy Scale. These scales utilize a scoring scheme in which a higher score indicates more knowledge and a more positive view of hospice, and more decision self-efficacy, respectively.

Description of surveys for primary outcomes:

- Knowledge of Hospice Test: The Knowledge of Hospice Test is a 23-item scale with true/false questions. The Cronbach's alpha coefficient for the scale is 0.75 showing good internal reliability.
- Decision Self-efficacy: Is an 11-item instrument that one's self-confidence in decision making. This scale is a validated scale with a Cronbach's alpha of 0.92 and correlates with DCS subscale of being informed ( $r=0.47$ ). Based on our prior study of a decision aid in palliative care, we hypothesize that one of the strongest effects of a decision aid might be to increase self-efficacy of the decision making.
- Hospice Beliefs and Attitude Scale (HBAS): The HBAS is an 8-item scale developed to measure beliefs and attitudes towards hospice care. It has a Cronbach's  $\alpha = .74$  for the scale, indicating a good degree of internal reliability.
- Demographic Form-a brief demographic form to record SES, age, sex and comorbidities such as diabetes, heart disease, and cancer.

Description of qualitative writing sample:

- Hospice knowledge will be qualitatively assessed prior to randomization at the baseline visit to better understand the misconceptions associated with hospice care. Matsuyama et al described a brief qualitative assessment in which participants are asked to describe "what is hospice" in their words. Participants will provide their answers on paper. These brief writings will be analyzed using thematic content analysis.

**B. Description of Population to be Enrolled:**

The target population are African American adults who are 65 years of age or older. Participants must be English speaking and self-identify as African American.

**C. Study Design and Research Methods**

Study Design: The study employs a two phase pre-/post-test intervention design or a small pilot randomized control trial (RCT), utilizing a one-to-one randomization scheme. Participants will be randomized into groups after completing the baseline assessments. Pilot RCTs are used to test the acceptance of a new intervention, as well as the feasibility of implementing a new intervention. The proposed study aims to test the efficacy of a paper and video decision aid for hospice care. The intervention group will receive both decision aids and the control group will receive no intervention. All participants will receive the intervention materials at the conclusion of the study regardless of intervention group.

Study Setting: Recruitment will take place at community organizations serving older African Americans and the outpatient primary care clinics for both UCHealth and Denver Health.

Recruitment: The target enrollment is 150 total (75 per arm) participants.

- Community Organizations-will consist of passive recruitment via flyers, listservs, electronic mailing mechanisms and advertisements in newsletters and newspapers.

- **Outpatient Clinics**- potential patients will be identified through weekly chart reviews. The study team will communicate with the outpatient physician by his/her preferred communication method (e.g. email, phone) to determine whether the patients are appropriate to be approached. If eligible and appropriate, a research team member will approach the patient and introduce the study following their clinical encounter. Flyers will also be hung in treatment rooms and common areas of each clinic. Reasons for non-approach will be recorded.
  - **Email/Mailings**-We will also review medical records for potentially eligible patients and send them either an email or letter via US mail describing the study and asking them to contact the study team if they are interested in participating.

**Research Methods:** This will be a 1:1 intervention:control randomization scheme.

- **Baseline Visit (Aim 1)**- All participants will complete the baseline measurements: brief writing exercise, the Hospice Knowledge Scale, Hospice Beliefs and Attitudes Scale (HBAS), and decision self-efficacy scale (all measurements described above). Additionally, all participants will be asked to briefly describe in writing “what is hospice” in their own words. Prior research shows this brief writing exercise exposes many of the misconceptions of hospice care and provides insights into overcoming knowledge barriers. A trained research assistant will be available to answer questions and provide clarification if necessary. Additionally, the participants’ preferred method of contact or phone number will be recorded for the follow-up visit (Aim2). After completion of baseline surveys, participants will be randomized for Aim 2 of the study.
- **Follow-up Visits (Aim 2)** - Participants randomized to the intervention group will be asked to review the PtDAs within 1 week of the baseline visit. Each participant will be contacted one week after the Phase 1 visit to complete follow-up assessments by phone. All participants, regardless of study arm, will be called 1-month after the baseline visit to complete the follow-up surveys by phone. The control and intervention groups will complete the primary outcomes surveys (Hospice Knowledge, decision self-efficacy & HBAS). The proposed intervention and follow-up are consistent with other shared decision making and PtDA studies.

**Data collection:** For patients who agree to participate, the study coordinator will collect baseline demographic and quantitative data (surveys described above in Section A). The research coordinator will then open the envelope to determine the patient’s allocation. Control patients will be asked to complete the baseline measures at time of enrollment and again at 1-month follow-up. Intervention patients will be given the decision aid and asked to review it within the next week. Then the best way to contact participants for follow-up calls will be recorded. Finally, each participant (control and intervention) will be contacted at one month for the final data point collection. \$25 gift cards will be given for baseline and one-month follow-up surveys.

- **Baseline visit (control & Intervention)**- All participants will be asked to complete the brief writing exercise, REALM test, Hospice Knowledge Test, Hospice Attitudes and Beliefs Scale, Decision Self-efficacy scale, and demographics.
- **One Week Follow-up call (intervention only)**-Participants will be asked to complete the Hospice Knowledge Test, Hospice Beliefs and Attitudes Scale, Decision Self-efficacy scale, the decision aid acceptability scale and brief decision aid feasibility questionnaire.
- **One Month Follow-up (control & intervention)**-At one month follow-up all participants will be asked to complete the Hospice Knowledge Test, Hospice Beliefs and Attitudes Scale, and the Decision Self-efficacy scale.

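### The one-month phone knowledge test could be open-book in the intervention arm only, and the plan neither asks for answers from memory nor records look-up

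*Combined protocol and SAP*

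**What the plan says.** **Instrument.** Section IV.A names three primary outcomes: hospice knowledge, beliefs and attitudes (HBAS), and decision self-efficacy. On the first it says: "The Knowledge of Hospice Test is a 23-item scale with true/false questions".

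**Who has the aids.** Section IV.C, Study Design: "The intervention group will receive both decision aids and the control group will receive no intervention". Controls wait until the end: "All participants will receive the intervention materials at the conclusion of the study regardless of intervention group".

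**How the aids are used.** Section IV.C, Data collection: "Intervention patients will be given the decision aid and asked to review it within the next week". Review is thus in the participant's own time. Nothing says that the materials are returned or how the video is supplied.

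**How the outcome is taken.** Section IV.C, Follow-up Visits (Aim 2): "All participants, regardless of study arm, will be called 1-month after the baseline visit to complete the follow-up surveys by phone". Those surveys include the knowledge test. The baseline test is taken at a visit, before randomisation, with a research assistant available.

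**One-week call.** The Follow-up Visits paragraph has each participant contacted at one week. The visit list later in Section IV.C limits that call to the intervention arm and includes the knowledge test in it.

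**Safeguards.** No section asks participants to answer without materials or records whether materials were used. Section IV.E (Potential Scientific Problems) deals with literacy and language only. Section IV.F (Data Analysis Plan) does not mention the issue.

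**The concern.** A true/false knowledge item has a right answer that a booklet may contain. On the phone, the caller cannot see whether the booklet is open. If some intervention participants consult it, their scores rise for a reason other than what they know, and controls have no study material to consult.

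The possible error runs in one direction, towards the aid. Randomisation does not balance it, because assignment is what creates the difference in access. Taking change from baseline does not remove it, because neither arm had the aid at baseline. Section IV.G says that the study is to supply pilot data for a multi-site trial, including on whether decision aids improve knowledge, so an inflated knowledge difference could carry forward into that planning.

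**Working it through.** **1. The plan's own figure.** Section IV.F gives a total of 150, alpha 0.05 and effect size 0.5. It states no power, sidedness or dropout, so 150 has no unique derivation. With 75 per arm, two-sided alpha 0.05 and a standardised effect of 0.5, a t-test has 86% power. Alternatively, 80% power needs 63 per arm (normal approximation) or 64 (t). Dividing 126 or 128 by 0.85 for an assumed 15% dropout gives 149 or 151. The figure of 150 is plausible, and the point does not depend on it. Only the 0.5 is used below, as a yardstick.

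**2. Access by arm at each knowledge test** (the plan's several names for the knowledge measure are taken as one instrument)

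| Test | Mode | Intervention arm | Control arm |
|---|---|---|---|
| Baseline | visit | no aid yet | no aid |
| One week | phone | aids given | no aid (whether called is unclear) |
| One month | phone | aids given, no return stated | no aid |

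The arms differ in access at the one-month test, the only post-baseline test that is clearly planned in both.

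**3. Size of the possible shift.** Let *f* be the share of the intervention arm that consults the aid during the call, *g* the items gained over what the same person would score from memory, and *s* the score SD. None of these is in the documents. The assumed ranges are *f* = 2% to 30%, *g* = 3 to 5 items, *s* = 3 to 5 items.

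Spurious difference = *f* × *g* items = *f* × *g* / *s* in SD units.

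- Smallest: 0.02 × 3 = 0.06 items; 0.06 / 5 = 0.012 SD.
- Largest: 0.30 × 5 = 1.5 items; 1.5 / 3 = 0.50 SD.

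Against the planned 0.5, that is from about 2% (0.012 / 0.5) to 100% (0.50 / 0.5).

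**4. Effect on the t-test if the aid truly does nothing for knowledge.** With 75 per arm and no dropout, SE = √{[*s*² + *s*² + *g*²*f*(1 − *f*)] / 75}. The noncentrality is *fg* / SE, with 148 degrees of freedom and two-sided 0.05.

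| *f* | Shift in SD (*g* = 3, *s* = 5 to *g* = 5, *s* = 3) | False-positive rate |
|---|---|---|
| 2% | 0.01 to 0.03 | 5.1% to 5.5% |
| 10% | 0.06 to 0.17 | 6.5% to 16% |
| 20% | 0.12 to 0.33 | 11% to 45% |
| 30% | 0.18 to 0.50 | 19% to 76% |

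Example for the last cell: SE = √[(9 + 9 + 25 × 0.21) / 75] = 0.557; noncentrality = 1.5 / 0.557 = 2.69; rejection rate 76%.

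The result depends almost wholly on *f*. At 2% the problem is negligible; at 30% it could account for the whole planned effect. The documents cannot place the trial on this range.

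**The case against.** **Look-up is conjecture.** Nothing in the documents suggests that participants do it. Possession at one month is inferred from own-time review with no return step. The call script is not reproduced, so its wording is unknown. The gift cards have no stated link to score. Finding answers in a booklet during a live call is awkward, and in a video more so. Look-up also helps only where the aid covers the item. All of this stands. It limits the point to what the plan allows, and it is why the range above starts near zero.

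**Having the aid is part of the intervention.** Aim 2 concerns the effect of the materials on knowledge, and the plan never specifies unaided recall. It also describes its intervention and follow-up as consistent with other decision-aid studies. This stands in part. Even so, the stated outcome is change in hospice knowledge, and as planned the data could not separate knowledge from reading during the call.

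**Controls can look things up too.** They could use other sources, but not the study aids, so the difference in access remains.

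**Stronger readings that the documents do not support.** A reader might infer that the one-month difference will not measure knowledge, or that Aim 2 as a whole is compromised. Neither follows: look-up is only possible, and HBAS and decision self-efficacy have no answers to find. A reader might also infer that the one-week call newly reveals the test items. Both arms have already seen them at baseline, so at most the call adds one more exposure, and in one arm only if the visit list governs.

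**Conclusion.** The concern holds in limited form. The plan as written permits one of three primary outcomes to be measured open-book in one arm only, with any resulting error in favour of the aid. It contains nothing to discourage this or to detect it. The size is unknown: about 0.01 to 0.50 SD under shares, gains and SDs that are all assumed. No narrower figure can be defended from the documents. For a pilot this is a modest validity gap rather than a flaw in the design. It is worth closing because the remedy is cheap, and because look-up that is not asked about at the call cannot be reliably reconstructed later.

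**What to change.** 1. In every follow-up call, in identical words in both arms, open the knowledge test with a scripted request to put aside any written or video material about hospice and answer from memory.
2. After all scales are complete, ask both arms whether they consulted any hospice material during the questions. Report the proportion by arm.
3. Keep the primary analysis on all randomised participants as scored. If a sensitivity analysis resets the one-month scores of those who say yes to their baseline values, label it a worst-case bound. It also removes real learning, and it conditions on behaviour after randomisation that is likely to differ by arm.
4. Reconcile the two statements in Section IV.C on who receives the one-week call. If it is the intervention arm only, state that this arm has one extra exposure to the test items before one month.

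**Cost.** One sentence and one yes/no item in the call script, with no added visits or staff. The question relies on self-report and may understate look-up. It may also reveal allocation to the caller (the documents do not say whether callers are blinded), so it must come last.
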